The Impact of Topical Tranexamic Acid in Breast Reconstruction

Protocol Number: CC # 228012

Investigational Product(s): Topical Tranexamic Acid

Version Number: v4

Version Date: 1/26/24

[figure not shown]
IND Number: N/A

NCT Number: 05807074

Principal Investigator (Sponsor-Investigator)

[name]

University of California, San Francisco

Statistician

[name]

UCSF Surgery Biostatistics Core

Revision History

Version 2 08/12/2022

Version 3 09/27/2022

Protocol Signature Page

1. I agree to follow this protocol version as approved by the UCSF Protocol Review and Monitoring Committee (PRMC), Institutional Review Board (IRB), and Data and Safety Monitoring Committee (DSMC).
2. I will conduct the study in accordance with the International Council for Harmonisation of Technical Requirements for Pharmaceuticals for Human Use (ICH) Good Clinical Practices (GCP) and the applicable IRB, ethical, federal, state, and local regulatory requirements.
3. I certify that I, and the study staff, have received the required training to conduct this research protocol.
4. I agree to maintain adequate and accurate records in accordance with IRB policies, federal, state and local laws and regulations.

UCSF Principal Investigator

[name]

Printed Name

DocuSigned by:

A redacted signature field, indicated by a black rectangular box with a blue border.

Signature

1/26/2024

Date

Abstract

Title	The impact of topical Tranexamic Acid in reconstructive post-oncologic breast surgery
Study Description	Improvement in bleeding and bruising has been described by using both intravenous and topical off-label applications of Tranexamic Acid (TXA) in many surgical fields. The proposed prospective study will evaluate the utility of topical tranexamic acid in decreasing hematoma and seroma rates, drain output, and ecchymosis in post-mastectomy breast reconstruction patients. This novel use of TXA in breast surgery may provide a simple, cost-effective, and safe way to improve outcomes and satisfaction for our breast cancer patients.
Phase of Study	Phase 2
Investigational Products	Tranexamic Acid (Topical application)
Study population	Female patients > 18 years old undergoing bilateral mastectomy with reconstruction or complex closure
Primary Objective	To investigate whether topical tranexamic acid may impact rates of seroma, hematoma, severe bruising, and drain output in the post-mastectomy reconstructive population
Sample Size	The goal enrollment is 150 patients undergoing bilateral mastectomy, or 300 breasts. Given that the literature cites a hematoma rate of up to 5% in post mastectomy patients, if we aim for complete reduction with TXA, we will need at least 150 per group to be adequately powered to detect that difference (alpha 0.05, beta 0.2). However, since complete reduction is not realistic, we will aim to recruit as many as possible with a minimum goal of 150 patients, which will give us 300 breasts total such that 150 breasts will receive TXA and 150 breasts saline.
Duration of Study Treatment	Participants will only be treated intraoperatively at the time of surgery with topical TXA to one breast pocket.

Duration of Follow up	We routinely follow post-mastectomy patients up to 1 year after their surgery. The standard post-operative follow-up regimen includes appointments at 1 week, 2 weeks, 6 weeks, 3 months, and 1 year, followed by yearly appointments thereafter. However, the schedule and number of visits will vary by patient. Patients in this study will be assessed at their regularly scheduled visits up to one year post-operatively.
Unique Aspects of this Study	This study is the first in the United States to evaluate the impact of topical Tranexamic Acid on hematoma, seroma, drain output, drain duration, and subjective bruising following post-mastectomy breast reconstruction, utilizing each patient as their own internal control.

List of Abbreviations

AE	Adverse Event
SAE	Serious Adverse Event
DSMC	Data and Safety Monitoring Committee
HDFCCC	Helen Diller Family Comprehensive Cancer Center
HIPAA	Health Insurance Portability and Accountability Act
IRB	Institutional Review Board
IV	intravenous
TXA	Tranexamic Acid

Table of Contents

Protocol Signature Page	2
Abstract	3
List of Abbreviations	5
Table of Contents	Error! Bookmark not defined.
1 Introduction.....	8
1.1 Background on Indication.....	8
1.2 Background on the Investigational Product(s) and Associated Known Toxicities	8
1.3 Rationale for the Proposed Study	9
1.4 Rationale for the TXA Dose Selection/Regimen	9
2 Study Objectives.....	10
2.1 Hypothesis.....	10
2.2 Primary Objective and Endpoint(s).....	10
2.3 Secondary Objective(s) and Endpoint(s).....	11
3 Study Design	11
3.1 Characteristics.....	11
3.2 Sample Size	12
3.3 Eligibility Criteria.....	12
3.3.1 Inclusion Criteria	12
3.3.2 Exclusion Criteria	13
3.4 Inclusion of Women and Minorities	13
3.4.1 Eligibility of Women and Minorities	13

1.1 Background on Indication

Post-mastectomy breast reconstruction has significant physical, mental and emotional benefits for breast cancer patients[1]. However hematoma, seroma and bruising are common complications given the highly vascularized nature of breast tissue[2]. These events can compromise the reconstruction, as well as potentially delay cancer treatments including chemotherapy and radiation by predisposing the patient to infection and wound complications. The hematoma and subsequent reoperation rate in breast surgery has been cited from 2-5% [2], thus topical hemostatic agents are often used intraoperatively. However, these agents are usually expensive, come in varying forms, and difficult to regulate. Prior studies in orthopedics, plastic surgery, and trauma have shown a significant reduction in bleeding, ecchymosis, and need for transfusions with use of Tranexamic Acid (TXA)[3-12]. TXA is a synthetic amino acid that blocks plasminogen conversion to plasmin, to prevent fibrinolysis and stabilize clot formation. Improvement in bleeding and bruising has been described utilizing both intravenous and topical off-label applications of TXA[6, 12]. In breast surgery there have been mixed results to preliminary retrospective studies of both intravenous and topical tranexamic acid, with some decreases in hematoma and seroma rates, and drain volumes[13-15]. The proposed prospective trial will evaluate the efficacy of topical TXA in decreasing hematoma and seroma rates, drain output, drain duration, and ecchymosis in bilateral post-mastectomy breast reconstruction patients. Every patient will serve as their own control. This novel use of TXA in breast surgery may provide a simple, cost-effective, and safe way to improve outcomes in breast reconstruction patients.

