2.2 Primary Objective and Endpoint(s)

The primary objective of this study is to evaluate the impact of topical TXA versus control (saline) on key post-operative outcome measures. These include hematoma, seroma, drain output, drain duration, bruising, and reoperation.

Primary Objective	Endpoint(s)	Time Frame
1. To evaluate the impact of TXA on hematoma rates compared to control	Presence of hematoma in 30 day period	From application in the operating room to 30 days of follow up
2. To evaluate the impact of TXA on seroma rates compared to control	Presence of seroma in 3 month period	From application in the operating room to 3 months of follow up

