3.1 Characteristics

We propose a prospective, placebo-control trial looking at the effect of topical tranexamic acid on post-operative bleeding, hematoma, seroma, drain output, and bruising in post-mastectomy breast reconstruction. We will recruit patients undergoing bilateral mastectomy at our institution. Patients will be excluded if they have previous history of bleeding or coagulation disorders. Each patient will serve as their own internal control, with one side receiving saline and the other TXA. During surgery and prior to wound closure, we will moisten the wound surface of one side with 20 cc of dilute TXA 25mg/ml solution, and the contralateral with 20cc of saline. Demographics, cancer details, and surgical characteristics will be collected. Outcomes will we assess include hematoma, seroma, reoperation, drain duration, and degree of ecchymosis will be recorded post-operatively for analysis over a 3-month period. The primary outcome will

be presence of hematoma. Secondary outcomes will include seroma, drain output and duration, ecchymosis, and return to operating room.

The surgeon will mix the TXA solution and pass onto the surgical field (detailed in a later section). After completion of the bilateral mastectomy, the plastic surgeon will perform their portion of the procedure. Immediately prior to final closure, 20ml of 25mg/ml TXA solution will be infiltrated into one breast pocket. 20ml of 0.9% normal saline will be infiltrated into the other breast pocket. No other hemostatic agents will be used. The sidedness of the TXA administration will be documented by the surgery team in our record but kept confidential from the surgery clinic staff to prevent bias at post-operative assessments. The solutions will be allowed to dwell while performing incisional closure, and the solutions will be evacuated by the Jackson-Pratt drain when placed to bulb suction at the end of the case. Post-procedure, each patient will be provided with standard post-operative instructions. They will be followed post-operatively for up to 1 year.

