7.2 Safety Analysis

Safety will be assessed by clinically assessing for signs of intolerance or irritation after administration of the TXA. If there are any immediate adverse effects noted related to sensitivity reactions, the JP drain will be placed to suction and the TXA solution removed and washed out via infiltration of plain saline to the breast pocket. We will assess patients at each post-operative visit with condition-specific physical exam and history to make sure there are no other adverse effects noted. If any thrombotic complications are found with no other explanation, we will deem the study unsafe and stop the study.

8 Study Management

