9.2.2 Attribution

Adverse events are given an assignment of attribution or relationship to the investigational agent(s) or study procedure. Attribution categories are:

- Definite – The adverse event is clearly related to the investigational agent(s) or study procedure.

- Probable – The adverse event is likely related to the investigational agent(s) or study procedure.
- Possible – The adverse event may be related to the investigational agent(s) or study procedure.
- Unrelated – the adverse event is clearly not related to the investigational agent(s) or study procedure.

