3.1 Adverse Event Monitoring

All Grade 3-5 adverse events (AEs), whether or not considered to be expected or unexpected and whether or not considered to be associated with the use of the investigational agent(s) or study procedure, will be entered into OnCore®, UCSF's Clinical Trial Management System.

Adverse events are graded according to the Common Terminology Criteria for Adverse Events (CTCAE) as developed and revised by the Common Therapy Evaluation Program (CTEP) of the National Cancer Institute. Adverse events are further given an assignment of attribution or relationship to investigational agent or study procedure. Attribution categories are:

- **Definite** – clearly related to the investigational agent(s) or study procedure.
- **Probable** – likely related to the investigational agent(s) or study procedure.
- **Possible** – may be related to the investigational agent(s) or study procedure.
- **Unrelated** –clearly not related to the investigational agent(s) or study procedure.

All Grade 3-5 adverse events entered into OnCore will be reviewed on a monthly basis at the Site Committee meetings. The Site Committee will review and discuss the selected toxicity, the toxicity grade, and attribution assignment.

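### Local adverse events outside the section 7.1 outcome list, such as irritation and wound complications, are neither recorded nor compared by breast, so the safety analysis cannot separate a local TXA effect from surgical background

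*Combined protocol and SAP*

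**What the plan says.** The design is within-patient. The background in 1.1 puts it this way: "Every patient will serve as their own control. This novel use of TXA in breast surgery may provide a simple, cost-effective, and safe way". Section 3.1 states: "Each patient will serve as their own internal control, with one side receiving saline and the other TXA". The objective in 2.2 is comparative: "The primary objective of this study is to evaluate the impact of topical TXA versus control (saline) on key post-operative outcome measures". Section 3.1 adds: "Secondary outcomes will include seroma, drain output and duration, ecchymosis, and return to operating room".

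Section 7.1 lists the post-operative outcomes to be collected (hematoma, seroma, infection, reoperation, and aspiration or drain placement in clinic or radiology) and plans to compare outcomes between TXA and saline breasts. Bruising is also compared by side (2.3 and 7.1).

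Safety is handled separately. Section 7.2 begins: "Safety will be assessed by clinically assessing for signs of intolerance or irritation after administration of the TXA". It then describes examination and history at follow-up visits and a rule for thrombotic events. Section 9.2.2 says: "Adverse events are given an assignment of attribution or relationship to the investigational agent(s) or study procedure". Appendix 1, section 3.1, sets the entry rule for OnCore: "All Grade 3-5 adverse events (AEs), whether or not considered to be expected or unexpected", whatever the attribution. Appendix 1, section 3.2, adds serious events. Section 9.3 does not count edema and ecchymosis below Grade 3 as adverse events. None of these sections mentions the side of an event or a summary by breast.

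**The concern.** The saline breast is the natural comparator for local harm, because it has the same patient, operation and follow-up. For local events outside the 7.1 list, the plan relies on clinical assessment after TXA and on attribution of each event. Neither can do what a comparison does:

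- If the rater knows the treated side, an event in the TXA breast can be rated possibly related to the agent. The same event in the saline breast cannot be a local effect of TXA. The ratings then partly reflect the side.
- If the rater is masked, as 3.1 and 6.3 intend for clinic staff, the rating of a single event carries no information on whether TXA raised its frequency.

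In both cases only counts by side answer the question. Without them, background events in TXA breasts may be read as harm, or a real excess may be dismissed as background. If side is not noted at the time, it may be hard to recover later.

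**Working it through.** **Step 1. Which local events are compared with the saline breast?**

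| Local event | TXA v saline comparison planned? | Where |
|---|---|---|
| Hematoma, seroma | Yes | 2.2, 7.1 |
| Infection, reoperation, aspiration or drainage | Yes | 7.1 |
| Bruising | Yes, which side is worse | 2.3, 7.1 |
| Irritation or intolerance | No | 7.2 |
| Other wound complications | No | mentioned in 1.1; only the general adverse event rules apply |

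The gap is the last two rows. Irritation is a measure that 7.2 itself chooses for safety.

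**Step 2. Is the information within reach?** The calendar in 6.1 schedules an adverse event assessment during surgery and in all three post-operative windows. Section 7.1 keeps an encrypted record of the solution given to each breast. Only the side of the event is missing.

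**Step 3. Number of pairs.** Sections 3.2 and the Abstract give 150 per group for 5% v 0% (alpha 0.05, beta 0.2). The two-sided unpooled formula gives n = (1.96 + 0.8416)² × (0.05 × 0.95 + 0) / 0.05² = 7.849 × 0.0475 / 0.0025 = 149.1, rounded up to 150. The pooled version gives 152. The figure reproduces and is not in dispute. It supplies 150 pairs.

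**Step 4. Precision of a paired comparison.** The documents give no rate for these events, so the rates below are assumptions. With equal true rates p on both sides, independent within patient, the half-width of the 95% interval for the difference is 1.96 × √(2p(1 − p)/150).

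| Assumed rate per side | Expected breasts with an event, per side | Half-width |
|---|---|---|
| 5% | 150 × 0.05 = 7.5 | 1.96 × √(0.095/150) = 4.9 points |
| 10% | 150 × 0.10 = 15 | 1.96 × √(0.18/150) = 6.8 points |
| 15% | 150 × 0.15 = 22.5 | 1.96 × √(0.255/150) = 8.1 points |

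At 10% and no effect, about 15 TXA breasts would have an event. Seen alone, that count cannot be interpreted. Set against about 15 saline breasts, it gives an excess near 0 with an interval of about ±6.8 points. Positive correlation between a patient's two breasts would narrow the interval.

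**Step 5. Could it serve as a test?** Power of an exact two-sided McNemar test with 150 pairs and independent sides:

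| Saline v TXA rate (assumed) | Power |
|---|---|
| 2% v 4% | 9% |
| 2% v 6% | 32% |
| 5% v 10% | 30% |
| 5% v 15% | 78% |
| 10% v 15% | 20% |
| 10% v 20% | 63% |

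The half-width across these six cases runs from 3.9 to 8.0 points. The comparison is informative as an estimate but too weak to be a confirmatory test.

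**The case against.** The strongest reply is that the main local complications are already compared by breast. Section 7.1 does so for infection, hematoma, seroma, reoperation and aspiration or drainage. A wound problem serious enough to need reoperation or drainage enters that comparison. This stands, and it limits the point to the remaining local events.

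Four stronger readings are tempting but not supported:

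- A reader might infer that local harms are never compared between sides, or that the saline breast is ignored. Section 7.1 contradicts that.
- A reader might infer that the trial sets out to demonstrate safety. Section 1.1 says only: "This novel use of TXA in breast surgery may provide a simple, cost-effective, and safe way to improve outcomes in breast reconstruction patients". Sections 2.1 to 2.3 contain no safety hypothesis, objective or endpoint. Section 1.1 also mentions wound complications as a consequence of hematoma, seroma and bruising, not as a TXA harm to be tested.
- A reader might infer that saline-side events are unrelated by definition. Section 9.2.2 also rates relation to the study procedure, and instilling saline is part of that procedure.
- A reader might infer that a biased count of related events will be reported, as large as the whole background rate. No section plans such a count, attribution does not filter which Grade 3-5 events are entered, and the documents do not say who assigns attribution or whether that person knows the side.

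It can also be said that recording Grade 1-2 events goes beyond the institutional Grade 3-5 entry rule. That is true, and it is the cost of the change. But irritation will often fall below Grade 3, so that rule alone would leave much of what 7.2 looks for outside any tabulation.

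**Conclusion.** The point holds in a limited form. For local adverse events outside the 7.1 list, the plan specifies no recording by side and no comparison with the saline breast. Its method of clinical assessment after TXA plus attribution cannot separate a local drug effect from surgical background, although the design supplies the comparator. The primary hematoma comparison and the other 7.1 comparisons are unaffected.

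The gain is a descriptive estimate with a half-width of about 6.8 points at an assumed 10% rate per side, and 4.9 to 8.1 points over assumed rates of 5% to 15%. This takes 150 complete pairs and independent sides.

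Two limits apply. Systemic harms have no within-patient control, because section 3.6 gives TXA to every patient. And any analysis by side requires the treated side to be unambiguous. Section 6.3 places TXA in the right pocket, while the calendar in 6.1, as it reads in the available text, carries its mark on the left breast row. These must be reconciled.

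**What to change.** 1. At the adverse event assessments already in 6.1, record the side (right, left, both, systemic) of each local adverse event and wound complication noted at the examination, whatever its grade. Clinic staff record right or left only, so masking to treatment is kept.
2. In 7.2, link side to treatment at analysis using the record described in 7.1. Tabulate breasts with at least one event, TXA v saline, by event type and grade. Give the paired difference with a 95% interval, labelled as a descriptive local-safety summary. Keep attribution as supporting information.
3. State in 7.2 that systemic events are reported for all patients without a within-patient comparison.
4. Before doing so, reconcile sections 6.1 and 6.3 on the treated side.

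The cost is one field on the adverse event form, one table, and a little more recording of low-grade local events. No extra visits are needed.

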1.2 Background on the Investigational Product(s) and Associated Known Toxicities

TXA is a synthetic amino acid that blocks plasminogen conversion to plasmin to stabilize clot formation [16]. Despite the fact that TXA is only FDA-approved for hemophilia patients to reduce hemorrhage and need for replacement therapy following tooth extraction [16], many high powered double-blind randomized trials have published their results using TXA in other surgical specialties. Prior orthopedic arthroplasty studies have shown that a single intraoperative dose of TXA prior to incision significantly decreases blood loss and transfusion requirements without associated thrombotic complications [6, 7, 11, 17]. These have shown that not only intravenous, but also directly infiltrating the joint topically can decrease bleeding [6, 12]. Furthermore, there have not been any report of increased systemic thrombosis when used topically. In plastic surgery, TXA is routinely dosed intravenously prior to incision for pediatric craniosynostosis cases to minimize blood loss, decrease transfusion requirements, and shorten length of hospital stay [3, 4, 9]. The literature also shows when used topically it can significantly decrease bruising and bleeding in rhinoplasty, rhytidectomy, and liposuction [8, 10, 18, 19].

More recently, there have been retrospective studies in breast plastic and oncologic surgery evaluating the use of TXA without any evidence of thrombotic complications. Weissler et al published a retrospective review of immediate post-mastectomy tissue

expander placement which showed a statistically significant decrease in hematoma with intravenous TXA administration[13]. Perhaps most pertinent for our study is the small trial from Ausen et al in the Netherlands in which they examined topical moistening of mastectomy flaps with a dilute TXA solution. They found no complications were related to topical administration of TXA relative to the control group[15]. This small study trended toward decreasing hematoma rates and drain volumes, and inspired our own study design of using each patient as their own internal control. We hope to build off this study given our large volume of mastectomies, and low risk profile of utilizing topical TXA. Additionally, designing the study such that each patient receives a control and experimental dose (saline on one side, TXA on the other) will help us to control for any confounding patient factors and further validate our results.

Given the mechanism of action of TXA, there is the theoretical complication of perpetuating thrombotic events due to inhibition of clot breakdown[16]. There have been no documented events of venous thromboembolism in relation to topical administration of TXA in plastic surgery procedures, which are the most relevant to our proposed study[6, 8, 14, 15, 18]. One prior study in trauma patients showed an increased risk of pulmonary embolism/or deep venous thrombosis with TXA[20]. However, this was a study regarding repetitive intravenous dosing, and in a uniquely sick patient population in extremis, with disseminated intravascular coagulation due to acute traumatic blood loss and therefore not directly applicable to our proposed study. Other side effects associated with intravenous tranexamic acid include hypersensitivity reactions, seizures, visual disturbances, and dizziness[16]. The latter three would not apply to our study given that with topical tranexamic acid, the drug will not cross the blood brain barrier and thus would not elicit neurologic adverse effects.

